### **8.1.1 Efficacy Analyses**

The all-patients-treated (APT) population will serve as the primary population for the analyses of efficacy data in this trial. ORR based on RECIST 1.1 assessed by independent radiology review is the primary efficacy endpoint. A point estimate and a 95% confidence interval (as determined by the upper and lower 97.5% one-sided confidence bounds) based on the exact binomial distribution will be provided in all subjects, PD-L1 positive, and PD-L1 strongly positive populations. No hypothesis testing will be performed. An outline of the efficacy analysis strategy is presented in [Table 8](#).

### **8.1.2 Safety Analyses**

The APT population will be used for safety analyses. Safety will be summarized for all subjects treated.

### **8.1.3 Power and Sample Size**

The sample size of this study is driven by the requirement for adequate efficacy evaluation for the PD-L1 strongly positive population. It is expected that ~350 subjects will be enrolled, which will provide enough subjects for the PD-L1 strongly positive population.

### **8.1.4 Biomarker/Interim Analysis**

The biomarker analysis to establish the PD-L1 strongly positive cutpoint is planned. An interim futility analysis is planned for the PD-L1 negative population within the biomarker discovery population. See 8.2.9 for more details.

## **8.2 Statistical Analysis Plan**

### **8.2.1 Responsibility for Analyses/In-House Blinding**

The statistical analysis of the data obtained from this study will be the responsibility of the clinical biostatistics department of the SPONSOR.

This trial is being conducted as an open-label non-randomized single-arm clinical trial. The trial has primary objectives in the subset of subjects that is PD-L1 positive, defined as a PD-L1 CPS score  $\geq 1\%$ , and PD-L1 strongly positive, defined as the PD-L1 CPS score  $\geq$  the optimal cut-point determined from data obtained from the biomarker discovery population. The study team will remain blinded to PD-L1 scores for individual patients throughout the study period until database lock for the primary study report; interim analyses related to PD-L1 scores will be conducted by a sponsor unblinded statistician.

The clinical biostatistics department will generate the allocation schedule for study treatment assignment. Allocation will be implemented in an interactive voice response system (IVRS).

## **8.2.2 Hypotheses/Estimation**

Objectives of the study are stated in Section 3.0. There is no hypothesis and the efficacy objectives are related only to estimation.

## **8.2.3 Analysis Endpoints**

Efficacy and safety endpoints that will be evaluated are listed below, followed by the descriptions of the derivations of selected endpoints.

### **8.2.3.1 Efficacy Endpoints**

The primary efficacy endpoint is objective response rate (ORR), defined as the proportion of subjects in the analysis population who have complete response (CR) or partial response (PR) using RECIST 1.1 criteria assessed by independent radiology review at any time during the study.

Secondary efficacy endpoints include:

- Duration of response (DOR) (RECIST 1.1 by independent radiology review).
- Overall survival (OS) and progression free survival (PFS) (RECIST 1.1 by independent radiology review).
- PFS (RECIST 1.1 by independent radiology review) rate and OS rate at 6 months and 12 months.

### **8.2.3.2 Safety Endpoints**

A description of safety measures is provided in Section 4.2.3.2.

The primary safety endpoints are AEs graded using CTCAE (Version 4.0) criteria. Safety will be assessed by quantifying the toxicities and grades experienced by subjects who have received MK-3475, including serious adverse events (SAEs) and events of clinical interest (ECIs). Immune-related ECIs, as described in Section 7.2.3.2, will be collected. Other safety endpoints include laboratory safety assessments, ECOG performance status, vital signs and physical examinations.

## **8.2.4 Analysis Populations**

### **8.2.4.1 Efficacy Analysis Population**

The APT population, which consists of all enrolled subjects who receive at least one dose of study treatment, will serve as the primary population for the analyses of efficacy data in this trial. Supportive analyses of efficacy will be conducted in the full analysis set (FAS) population, which consists of all enrolled subjects who receive at least one dose of study treatment and have measurable disease at baseline.

The biomarker discovery population, subjects in this trial used for the determination of the PD-L1 strongly positive cut-point, will be excluded from efficacy analyses for the PD-L1 strongly positive population. These subjects will still be included in the efficacy analyses for all and PD-L1 positive subjects.

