### **8.1 Statistical Analysis Plan Summary**

This section contains a brief summary of the statistical analyses for this trial. Full detail is in the Statistical Analysis Plan (SAP) (Section 8.2).

The primary and secondary objectives of this study include evaluations of the clinical efficacy of pembrolizumab (MK-3475) as 1L therapy in subjects with advanced/unresectable (inoperable) or metastatic urothelial cancer who are ineligible for cisplatin-based therapy, in all subjects, PD-L1 positive, and PD-L1 strongly positive (if applicable) populations, by objective response rates, response duration, PFS, and OS. The PD-L1 positive/negative population is defined as patients with PD-L1 IHC assay CPS score of at least/lower than the pre-specified PD-L1 positive cut-point of 1%. The PD-L1 strongly positive is defined as patients with CPS score of at least the PD-L1 strongly positive cut-point determined using the biomarker discovery population (first 100 enrolled excluding subjects not evaluable). If a PD-L1 strongly positive cut-off with clinical utility cannot be determined, only the all subjects and PD-L1 positive populations will be evaluated.

Analyses examining the association between PD-L1 expression and clinical efficacy to determine PD-L1 cut-point determination will be discussed in 8.2.5.3. The biomarker discovery population consists of the first 100 subjects enrolled; data from the biomarker discovery population will not contribute to efficacy evaluations for the PD-L1 strongly positive population.

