#### **8.2.4.3 Biomarker Discovery Population**

The biomarker analysis will be based on all subjects within the first 100 enrolled by time that are deemed clinically evaluable, which is defined as any subjects who received at least one dose of study drug and had week 9 and week 15 scans, or discontinued due to radiographic/clinical progression or death before reaching week 15. The biomarker discovery population will be identified through routine review of accumulating data.

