#### **8.2.5.1 Statistical Methods for Efficacy Analyses**

Efficacy will be available for PD-L1 strongly positive subjects, PD-L1 positive subjects, and all subjects. The first 100 study subjects (biomarker discovery population) will be evaluated for biomarker cut-point determination. The biomarker discovery population will be excluded from the primary and secondary objectives for the PD-L1 strongly positive subjects.

For the primary efficacy endpoint, the ORR based on RECIST 1.1 by independent radiology review, the point estimate, and 95% confidence interval (as determined by the upper and lower 97.5% one-sided confidence bounds) will be provided using an exact binomial distribution (Clopper and Pearson method). Subjects without response data will be counted as non-responders.

Duration of responses (DOR) based on RECIST 1.1 by independent radiology review will be summarized descriptively using Kaplan-Meier medians and quartiles. Only the subset of subjects who show a complete response or partial response will be included in this analysis. For PFS and OS, Kaplan-Meier (KM) curves, median estimates, and survival rates at 6 and 12 months based on the KM curves (95% CI is based on Greenwood's formula) will be

provided. Subjects without efficacy evaluation data or without survival data will be censored at Day 1.

A summary of the primary analysis strategy for the primary and secondary efficacy endpoints is provided in [Table 8](#).

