### **8.2.9 Interim Analyses**

A biomarker analysis is planned where data from a subset of subjects (the biomarker discovery population) will be used to determine the PD-L1 strongly positive cut-point. The biomarker discovery population consists of the evaluable subjects among the first 100 subjects enrolled into the study. Analysis will be conducted according to the SAP (section 8.2.5.3). More subjects may be allocated to the biomarker discovery population, if necessary.

In addition, an interim efficacy evaluation for the PD-L1 negative population will be performed using the biomarker discovery population data. Enrollment of PD-L1 negative (CPS  $< 1\%$ ) population may be stopped if the ORR is low and substantial enrollment remains. The futility analysis will be based on the evaluable PD-L1 negative subjects in the biomarker discovery population (up to the first 25 subjects). If the number of PD-L1 negative subjects in the biomarker subgroup is less than 20, additional PD-L1 negative subjects may be included until the number reaches at least 20. The non-binding rule for futility is the upper limit of the 95% CI (two-sided) of the ORR estimate is less than 20% (need at least 1 response in  $N < 26$  subjects, and at least 2 responses in  $N = 26$  to 40 subjects).

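### The SAP defines the biomarker discovery population two ways, so the denominator of the PD-L1 strongly positive ORR is not fixed

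*Combined protocol and SAP*

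**What the plan says.** Three places restrict the discovery population to evaluable subjects:

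- 8.2.4.3: "all subjects within the first 100 enrolled by time that are deemed clinically evaluable". Evaluable means at least one dose plus both the week 9 and week 15 scans, or discontinuation for progression or death before week 15. The section adds: "The biomarker discovery population will be identified through routine review of accumulating data".
- 8.2.9: "The biomarker discovery population consists of the evaluable subjects among the first 100 subjects enrolled into the study".
- 8.1, second paragraph: "first 100 enrolled excluding subjects not evaluable".

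Three places use all of the first 100:

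- 8.2.5.1: "The first 100 study subjects (biomarker discovery population) will be evaluated for biomarker cut-point determination". The next sentence excludes that population from the strongly positive primary and secondary objectives.
- 8.1, third paragraph: "The biomarker discovery population consists of the first 100 subjects enrolled".
- 8.2.7, which takes 100 for discovery out of 350 before computing how many strongly positive subjects remain for confirmation.

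The exclusion rule in 8.2.4.1 is tied to use: it removes subjects "used for the determination of the PD-L1 strongly positive cut-point, will be excluded from efficacy analyses" for the strongly positive population and keeps them in the all-subjects and PD-L1 positive analyses. The APT population in the same section requires only one dose. Section 8.2.9 also leaves the boundary open: "More subjects may be allocated to the biomarker discovery population, if necessary".

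**The concern.** The strongly positive ORR is one of the three primary objectives in 3.1, and 8.1.3 and 8.2.7 say it drives the sample size. Two analysts following different sections of the same SAP would report different denominators for it, and for DOR, PFS and OS in that population.

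The evaluable-only version also produces an odd confirmation group. It removes the evaluable members of the first 100 and puts back only their treated, non-evaluable peers, such as subjects who stopped for toxicity or withdrew consent and so lack a week 9 or week 15 scan. Their membership then depends on what happened after the first dose and is settled while data accumulate, whereas enrolment order would fix it in advance.

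**Working it through.** **Step 1. Trace one subject.** Take a strongly positive subject among the first 100 who was dosed, missed the week 15 scan, and had neither progressed nor died.

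| Sections followed | In discovery population? | In strongly positive ORR? |
|---|---|---|
| 8.2.4.1 with 8.2.4.3 and 8.2.9 | No (not evaluable) | Yes (in APT, not used for the cut-point) |
| 8.2.5.1 | Yes (among the first 100) | No |

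No other section settles the matter. Treating 8.1 as a summary only does not help, because the conflict lies within 8.2. Subjects never dosed are outside APT and do not matter here.

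**Step 2. Reproduce the plan's own figure.** From 8.2.7: 350 enrolled, 100 removed, prevalence 33%, so n = 350 − 100 = 250.

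- With p = 1/3: P(X ≥ 75) = 0.883 and P(X ≥ 60) = 0.9995, matching the stated 88% and 99.9%.
- With p = 0.33 exactly: 0.859 and 0.9992, so the plan appears to have rounded 1/3 to 33%.

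The sizing is therefore consistent with removing all 100. If k treated, non-evaluable subjects return, n = 250 + k, and P(X ≥ 75) at p = 1/3 becomes 0.920 (k = 5), 0.947 (k = 10) and 0.979 (k = 20). The larger group does no harm to precision; it is simply not the group that was sized.

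**Step 3. Effect on ORR.** The documents do not give k. I assume 5 to 20.

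- Base strongly positive group: 250/3 = 83.3.
- Added: 5/3 = 1.7 to 20/3 = 6.7, about 2 to 7 subjects.
- Resulting ORR = (ORR₀ × 83.3 + r × added) / (83.3 + added), where r is the response rate among the added subjects.

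| r | From ORR₀ = 30% | From ORR₀ = 40% |
|---|---|---|
| 0 | 29.4% to 27.8% | 39.2% to 37.0% |
| half of ORR₀ | 29.7% to 28.9% | 39.6% to 38.5% |
| 1.5 × ORR₀ | 30.3% to 31.1% | 40.4% to 41.5% |

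Each range runs from k = 5 to k = 20. The shifts are falls of 0.3 to 3.0 points or rises of 0.3 to 1.5 points.

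**Step 4. Set this against the precision.** Clopper-Pearson 95% intervals: 33/83 = 39.8% (29.2 to 51.1, width 21.9 points); with 7 added non-responders, 33/90 = 36.7% (26.8 to 47.5). From a row of Table 10, 25/75 = 33.3% (22.9 to 45.2) becomes 25/82 = 30.5% (20.8 to 41.6).

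**The case against.** The strongest defence is that 8.2.4.3 is the section that defines this population, 8.2.9 repeats it, and the phrase in 8.2.5.1 is shorthand. On that reading, excluding only subjects who informed the cut-point is principled: the others cause no cut-point reuse bias, and keeping every other treated subject follows the APT approach. The 100 in 8.2.7 would be a planning number only, and the probability match does not settle it, because at p = 0.33 exactly n = 252 gives 87.8%.

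Much of this stands. There is no reuse bias. It is the wording of 8.2.7, more than the matching probability, that shows 100 set aside. The trial is estimation only (8.2.2, 8.2.6), with no decision rule on this ORR. Section 8.2.1 keeps the study team blinded to individual PD-L1 scores until database lock, which limits any choice of definition after ORR is seen. A rise is also less likely than a fall: 8.2.5.1 counts missing response as non-response, and 7.1.2.6.2 calls for confirmation at least 4 weeks later, so a week 9 responder who missed week 15 is secure as a responder only if another scan confirms it.

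The defence does not remove the literal conflict with 8.2.5.1. Nor does the APT argument rescue the evaluable-only rule, since that rule keeps only the part of the first 100 selected by incomplete follow-up.

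**Conclusion.** The concern holds: two definitions are in force, and they give different denominators for a primary ORR. The consequence is modest: at most about 3 points under the assumed 5 to 20 non-evaluable subjects and one-third prevalence, against an interval about 22 points wide. The direction is uncertain, with a small fall more likely. Section 4.2.3.1.1 says response rates will be compared with a historical 30%, so a shift of this size could colour interpretation near that value, but nothing in Section 8 turns on it. Prevalence is held at 1/3; stopping PD-L1 negative enrolment under 8.2.9 would raise it. Effects on DOR, PFS and OS were not quantified. The point should be corrected because the contradiction is plain and cheap to remove, not because the bias is large.

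**What to change.** State in 8.2.4.1 that all of the first 100 enrolled subjects, together with any later subjects allocated to discovery under 8.2.9, are excluded from the strongly positive efficacy analyses whether or not they are evaluable. State also that those who received at least one dose stay in the all-subjects analyses and, if CPS is at least 1%, in the PD-L1 positive analyses. Keep the evaluability rule in 8.2.4.3 solely to select which of these subjects inform the cut-point. Align both paragraphs of 8.1, 8.2.5.1 and 8.2.9 with this. As an optional consistency edit, bring the contingency sentences in 2.1 and 4.2.3.3 on keeping cut-point subjects apart from the primary endpoint into line with 8.2.4.1.

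The change is to wording only; no data collection or sample size changes. Because it touches the analysis of a primary objective, the introduction to Section 8.0 would call for a protocol amendment. The statistical cost is the roughly 2 to 7 strongly positive subjects not used for confirmation, whom 8.2.7 already leaves out.

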#### **8.2.4.2 Safety Analysis Population**

The APT population will be used for the analysis of safety data. At least one laboratory or vital sign measurement obtained subsequent to at least one dose of study treatment is required for inclusion in the analysis of each specific parameter. To assess change from baseline, a baseline measurement is also required.

Details on the approach to handling missing data for safety analyses are provided in Section 8.2.5 Statistical Methods.

#### **8.2.4.3 Biomarker Discovery Population**

The biomarker analysis will be based on all subjects within the first 100 enrolled by time that are deemed clinically evaluable, which is defined as any subjects who received at least one dose of study drug and had week 9 and week 15 scans, or discontinued due to radiographic/clinical progression or death before reaching week 15. The biomarker discovery population will be identified through routine review of accumulating data.

### **8.2.5 Statistical Methods**

Statistical methods for efficacy and safety analyses are described in sections 8.2.5.1 and 8.2.5.2, respectively.

#### **8.2.5.1 Statistical Methods for Efficacy Analyses**

Efficacy will be available for PD-L1 strongly positive subjects, PD-L1 positive subjects, and all subjects. The first 100 study subjects (biomarker discovery population) will be evaluated for biomarker cut-point determination. The biomarker discovery population will be excluded from the primary and secondary objectives for the PD-L1 strongly positive subjects.

For the primary efficacy endpoint, the ORR based on RECIST 1.1 by independent radiology review, the point estimate, and 95% confidence interval (as determined by the upper and lower 97.5% one-sided confidence bounds) will be provided using an exact binomial distribution (Clopper and Pearson method). Subjects without response data will be counted as non-responders.

Duration of responses (DOR) based on RECIST 1.1 by independent radiology review will be summarized descriptively using Kaplan-Meier medians and quartiles. Only the subset of subjects who show a complete response or partial response will be included in this analysis. For PFS and OS, Kaplan-Meier (KM) curves, median estimates, and survival rates at 6 and 12 months based on the KM curves (95% CI is based on Greenwood's formula) will be

provided. Subjects without efficacy evaluation data or without survival data will be censored at Day 1.

A summary of the primary analysis strategy for the primary and secondary efficacy endpoints is provided in [Table 8](#).

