### **3.2 Secondary Objective(s) & Hypothesis(es)**

In subjects with advanced/unresectable or metastatic urothelial cancer who are ineligible to receive cisplatin-based therapy:

1. Objective: To evaluate the anti-tumor activity of pembrolizumab (MK-3475) as 1L therapy in PD-L1 strongly positive, PD-L1 positive and all subjects
  - By duration of response (DOR) based on RECIST 1.1 by independent radiology review.
  - By progression-free survival (PFS) based on RECIST 1.1 by independent radiology review and overall survival (OS).
  - By PFS rate based on RECICST 1.1 by independent radiology review and OS rate at 6 and 12 months.
2. Objective: To establish a cut-point for PD-L1 strongly positive status if this is not determined by other biomarker discovery populations, investigate the association between PD-L1 protein expression by IHC and anti-tumor activity.
3. Objective: To determine the safety and tolerability of pembrolizumab (MK-3475) as 1L therapy.

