- u. The initial tumor imaging at screening will be performed within 28 days prior to the first dose of trial treatment. Scans performed as part of routine clinical management are acceptable for use as the screening scan if they are of diagnostic quality and performed within 28 days prior to the first dose of trial treatment. Measureable disease based on RECIST 1.1 must be confirmed by central review before enrollment. All subjects will have a baseline bone scan performed at screening. Bone scans at baseline must be sent to central imaging vendor for review with initial tumor imaging to determine eligibility. Subjects with positive bone scans at baseline will be followed with additional scans performed at 9 weeks ( $\pm$  7 days) after the first dose of trial treatment on Day 1 Cycle 1, and then every 6 weeks ( $\pm$  7 days) thereafter or more frequently if clinically indicated. For subjects with new symptoms suggestive of osseous metastasis, a bone scan should be obtained. Additionally, plain X-ray evaluation should be obtained for symptomatic sites with negative bone scan evaluations. Refer to Section 7.1.2.6.3 of the protocol and site imaging manual.
- v. The first on-study imaging time point will be performed at 9 weeks ( $\pm$  7 days) after the first dose of trial treatment on Day 1 Cycle 1, and then every 6 weeks ( $\pm$  7 days) thereafter or more frequently if clinically indicated. After 12 months, imaging frequency should be reduced to every 12 weeks ( $\pm$  7 days). Imaging timing should follow calendar days and should not be adjusted for delays in cycle starts or extension of pembrolizumab (MK-3475) cycle frequencies. The same imaging technique should be used in a subject throughout the trial. On-study scans should be submitted immediately to the central imaging vendor; and progressive disease should be confirmed by the investigator/site radiologist prior to subject discontinuation from trial.
- w. In subjects who discontinue study therapy without confirmed disease progression, a radiologic evaluation should be performed at the time of treatment discontinuation (i.e., date of discontinue  $\pm$  4 week window). If a previous scan was obtained within 4 weeks prior to the date of discontinuation, then a scan at treatment discontinuation isn't mandatory.

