#### **7.1.2.6.2 Tumor Imaging During Trial**

The first imaging assessment should be performed at 9 weeks (63 days  $\pm$  7 days) after the first dose of trial treatment on Day 1 Cycle 1. Subsequent imaging should be performed every 6 weeks (42 days  $\pm$  7 days), more frequently if clinically indicated. Subjects who remain on treatment for a year will have imaging performed every 12 weeks (84  $\pm$  7 days). Imaging should not be delayed for delays in cycle starts or extension of pembrolizumab (MK-3475) cycle intervals.

Per RECIST 1.1, response should be confirmed by a repeat radiographic assessment not less than 4 weeks from the date the response was first documented. The scan for confirmation of response may be performed at the earliest 4 weeks after the first indication of response, or at the next scheduled scan (6 weeks later), whichever is clinically indicated.

Imaging should continue to be performed until disease progression, the start of new anti-cancer treatment, withdrawal of consent, death, or notification by the SPONSOR, whichever occurs first. Disease progression may be confirmed at least 4 weeks after the first scan indicating progressive disease in clinically stable subjects. Subjects who have unconfirmed disease progression may continue on treatment until progression is confirmed provided they have met the conditions detailed in Section 5.8.1.

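### The 6-month PFS rate is read from the Kaplan-Meier curve just as the week-27 scan window opens, so it overstates the proportion progression-free at 6 months; the size depends on assumptions the documents do not give

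*Combined protocol and SAP*

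**What the plan says.** Section 3.2 makes the PFS rate by "independent radiology review and OS rate at 6 and 12 months" a secondary objective. Section 8.2.3.1 repeats it as a secondary endpoint: PFS "rate and OS rate at 6 months and 12 months". Section 8.2.5.1 gives the method, "survival rates at 6 and 12 months based on the KM curves", with Greenwood intervals.

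On imaging, Section 7.1.2.6.2 states: "The first imaging assessment should be performed at 9 weeks" (63 days, within 7 days either side, from first dose), then every 42 days within 7 days, then every 12 weeks after a year. Section 6.1, note v, fixes the calendar: "Imaging timing should follow calendar days and should not be adjusted for delays in cycle starts".

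Table 8 names Kaplan-Meier for PFS and censors missing data at the last assessment. Nowhere does the plan convert 6 months to days, say how a progression found on a scan is dated, set a landmark window, or provide an interval-censored analysis.

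**The concern.** A Kaplan-Meier curve for scan-dated PFS stays nearly flat between scan windows, apart from deaths and off-schedule findings, and drops when scans are done. A reading just before a drop leaves out the progressions that have accumulated since the previous scan. The 6-month reading falls in that position; the 12-month reading falls just after a drop.

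The error runs in one direction, because a scan can record progression late but not early. Section 8.2.2 makes all efficacy objectives estimation only, so the point estimate and its interval are the whole result. There is no control arm in which the same lag would offset it. A larger sample narrows the interval without moving its centre back.

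**Working it through.** **Plan's own figure.** The documents state no PFS rate, median or PFS sample size, so there is nothing to reproduce.

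**Scan calendar** (Sections 7.1.2.6.2 and 6.1). Nominal scan days are 63 + 42k: 63, 105, 147, 189, 231, 273, 315, 357.
- Week 21: 147 ± 7, days 140 to 154.
- Week 27: 189 ± 7, days 182 to 196.
- Week 51: 357 ± 7, days 350 to 364.

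These windows are inferred from the stated steps. Six months by the usual conversion is 365.25/2 = 182.6 days, and 180, 182 or 183 days gives nearly the same result. Of the 15 days in the week-27 window, only day 182 precedes the reading. Twelve months (day 365.25) comes after day 364.

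**Approximate ceiling.** If no event after day 147 were yet recorded, the overstatement would be S(147) − S(182.6). With exponential PFS, S(t) = 2^(−t/median):

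| Median (months) | S(147) | S(182.6) | Difference (points) |
|---|---|---|---|
| 2 | 18.8% | 12.5% | 6.3 |
| 3 | 32.8% | 25.0% | 7.8 |
| 4 | 43.3% | 35.4% | 7.9 |
| 6 | 57.2% | 50.0% | 7.2 |
| 9 | 68.9% | 63.0% | 5.9 |

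**Simulation.** Deaths enter on their exact dates and some progressions may be caught off schedule, so the actual error is smaller. Assumptions, none of them from the documents:
- 400,000 subjects per setting;
- median PFS 2 to 9 months;
- 0, 15 or 30% of first events are deaths;
- 0 or 20% of progressions are caught at onset by an unscheduled scan;
- the rest are dated at the next scheduled scan, placed uniformly within its window.

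The error is the Kaplan-Meier reading minus the true proportion, in points:

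| PFS shape | Day 182.6 | Day 196 | 12 months |
|---|---|---|---|
| Exponential | +3.2 to +7.6 | +0.5 to +1.4 | +0.1 to +0.8 |
| Weibull, shape 0.7 | +2.4 to +5.3 | +0.4 to +1.0 | +0.2 to +0.6 |
| Weibull, shape 0.5 | +1.8 to +3.8 | +0.3 to +0.7 | +0.2 to +0.4 |
| 25% never progress, rest exponential | +1.3 to +5.8 | +0.2 to +1.0 | 0.0 to +0.6 |

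A separate exponential run that also counts deaths following an undetected progression gives +3.3 to +7.3 at day 182.6. One setting from that run: with a median of 3 months and 20% deaths, the true rate is 25.0% and the reading is 30.4 to 30.7%.

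**Share missing.** With no deaths and no unscheduled scans, roughly 80 to 90% of progressions between days 147 and 182.6 are not yet on the curve. With 30% deaths and 20% off-schedule detection, about half of all PFS events in that gap are missing (0.7 × 0.8 × 0.9 ≈ 0.50).

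**Scale.** Ignoring censoring, the 95% half-width is 1.96√(p(1−p)/n). At n = 350 it is 4.5 points for p = 0.25 and 5.2 for p = 0.50. At n = 225 it is 5.7 to 6.5, and at n = 75 it is 9.8 to 11.3.

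**The case against.** **The size is model-dependent.** This stands. Section 4.2.3.1.1 cites unusually long response durations with pembrolizumab, which suggests a falling hazard and fewer events between weeks 21 and 27. A reader might infer a fixed error of 4 to 7 points. The documents do not support that, because it needs a constant hazard and little or no off-schedule detection.

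**Off-schedule imaging is provided for.** This stands in part. Scans may be done earlier if clinically indicated. Unscheduled images showing progression go to the central vendor (Section 7.1.2.6). There is a scan at discontinuation (Section 6.1, note w). A confirmatory scan 28 days after week 21 would fall on day 175. All of these reduce the error, but no frequency is given and none removes it.

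**The window could attach to each interval.** If every 42-day step carries its own tolerance, scans drift. In the same simulation the day-182.6 error then runs from about 1 to 6 points, and the 12-month error rises to as much as 1.9. The calendar-day instruction favours fixed dates but does not settle the matter.

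**Kaplan-Meier estimates documented progression, which is the endpoint as defined.** This is true, and reading it at fixed months is conventional. A figure for documented progression nevertheless depends on where the scans fall, and the two landmarks sit differently against the calendar.

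**Nothing hangs on it.** No decision rests on PFS, and the only outside comparison the protocol names is for response rate, against 30% (Section 4.2.3.1.1). A reader might infer that the PFS rate will be benchmarked externally or that the efficacy conclusion is compromised; the documents support neither. The full curves are also planned, so a drop at week 27 would be visible.

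**Conclusion.** The concern holds as a minor-to-moderate point about a secondary, estimation-only rate. The position of the 6-month reading follows from the stated schedule and the usual conversion of months to days. The upward direction follows once progression is dated at the detecting scan, a convention the SAP leaves unwritten.

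The size is conditional: about 3 to 7.5 points under exponential PFS with the ranges above, and about 1.5 to 5.5 points with a falling hazard or long-term non-progressors. At 350 subjects that runs from well inside the confidence half-width to somewhat beyond it. The 12-month rate is off by at most about 1 point on the fixed calendar, so the fall between the two landmark rates is partly a product of scan timing. ORR and OS are not touched.

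A reader might go further and conclude that the 6-month landmark should be replaced. The documents do not require that. It would change the objective in Section 3.2 and give up the conventional time point.

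**What to change.** In Section 8.2.5.1 and the PFS row of Table 8:
- keep the 6-month Kaplan-Meier rate as the stated endpoint;
- define 6 months in days, and state how a scan-detected progression is dated;
- add as sensitivity analyses an interval-censored (Turnbull) 6-month PFS estimate, using the last progression-free scan and the first scan showing progression, with deaths as exact times, and the Kaplan-Meier rate at day 196, labelled week 28;
- report both beside the 6-month figure.

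The two complement each other. The week-28 reading is simple and leaves at most about 1.4 points of error on the fixed calendar. The Turnbull estimate uses actual scan dates and so also copes with drift. Sections 3.2 and 8.2.3.1 and the OS rates stay as they are. If the analyses are added after results are known, Section 8.0 requires them to be identified as post hoc.

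The cost is one or two extra estimates from scan dates already collected, with no new visits or imaging, and a less favourable figure printed next to the conventional one.
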